10.1.4.2.2 Unexpected Adverse Reactions

Unexpected Adverse Reaction Definition

An unexpected adverse reaction is any untoward and unintended response that is related to the administration of the study drug at any dose that is not consistent with the applicable product information (eg, investigator's brochure for an unauthorized investigational medicinal product or summary of product characteristics for an authorized product).

All suspected unexpected serious adverse reactions (SUSARs) will be the subject of expedited reporting. The Sponsor and/or Syneos Health shall ensure that all relevant information about a SUSAR that is fatal or life-threatening is reported to the relevant competent authorities and IEC/IRB within 7 days after knowledge by the Sponsor of such a case and that relevant follow-up information is communicated within an additional 8 days. All other SUSARs will be reported to the relevant competent authorities and IEC/IRB within 15 days after knowledge by the Sponsor of such a case. All investigators should follow up SUSARs until the event is resolved or until, in the opinion of the investigator, the event is stabilized or determined to be chronic. Post

study SUSARs that occur after the subject has completed the clinical study must be reported by the investigator to the Sponsor.

10.1.4.2.3 Clinical Laboratory Evaluation

The hematology and clinical chemistry laboratory analyses will be performed at a central laboratory (Q² Solutions). Reference ranges will be supplied and used by the investigator to assess the laboratory data for clinical significance and pathological changes. The following laboratory safety tests will be performed at Screening, during treatment, and at the end of treatment. **Results from Screening visit must be reviewed by the investigator before patient is randomized.**

Hematology

The following will be evaluated: hemoglobin, hematocrit, white blood cell (WBC) count (total and differential), red blood cell (RBC) count, platelet count, mean cell volume (MCV), mean cell hemoglobin (MCH), and mean cell hemoglobin concentration (MCHC).

Clinical Chemistry

The following will be evaluated: creatinine, AST/SGOT, ALT/SGPT, alkaline phosphatase, lactate dehydrogenase (LDH), total bilirubin, albumin, total protein, sodium, potassium, chloride, glucose, uric acid, total cholesterol, triglycerides, calcium, and phosphorus.

10.1.4.2.4 Other Laboratory Variables

Screening for pregnancy will be performed (urine beta-human chorionic gonadotropin [β -HCG]) at Screening, for females only. Kits will be provided by the central laboratory.

Blood samples will be collected for PK and immunogenic (ie, anti-ranibizumab antibodies and NAb) testing, at Baseline, during treatment and, at the end of treatment; PK and immunogenicity assessments will be done by Syneos Health laboratory.

10.1.4.2.5 Vital Signs

Vital signs (blood pressure and heart rate) will be recorded at Screening, during treatment (except Week 2 [Visit 3]), and at the end of treatment in a standardized manner. Systolic and diastolic blood pressure and pulse rate will be measured after patients have been at rest (seated) for at least 5 minutes.

10.1.4.2.6 Ophthalmological Examination

At Screening, during treatment, and at the end of treatment, an ophthalmological examination will be performed. Any changes from Screening to end of treatment/study will be recorded.

IOP measurements will be conducted at all visits (except Visit 3 [Week 2]).

10.1.4.2.7 Other Safety Assessments

A PE will be performed at Screening (with body mass index) and at the End of Treatment/Early Termination Visit. A PE will consist of a routine evaluation of organ systems (including head, ears, eyes, nose, throat, neck, cardiovascular, pulmonary, abdomen, skin, extremities, neurological, lymph nodes, and musculoskeletal). At the Week 52/End of Treatment Visit, the PE will also include a query of the patient to determine if changes in his/her physical condition have occurred since the PE at Screening.

10.1.5 Appropriateness of Measurements

The efficacy and safety assessments planned for this study are widely used and generally recognized as reliable, accurate, and relevant to the disease condition.

10.1.6 Drug Concentration Measurements

The plasma levels of ranibizumab will be evaluated at Baseline, on Day 1 at 23 hours (\pm 60 minutes) after the first dose, and at steady-state at Week 20 at 23 hours (\pm 60 minutes) after the sixth dose to detect any notable differences in systemic exposure between the 2 products, Xlucane and Lucentis[®]. The assay will be developed with sufficient sensitivity to be able to detect the differences at such low plasma levels.

10.2 Stopping Rules

The estimated duration of the study is contingent on safety and the number of injections evaluated. The study will be stopped in the event of any new findings that indicate a relevant deterioration of the risk-benefit relationship that would render continuation of the study unjustifiable. Study treatment will be halted, and the appropriate individuals from the Sponsor and Syneos Health will determine if the study should be terminated for any safety concerns.

The Sponsor may also end the study for administrative reasons.

Should the study be terminated prematurely, the Sponsor will provide written notification to all investigators and regulatory authorities specifying the reason(s) for early termination. The investigator must inform the Independent Ethics Committees

(IECs)/Institutional Review Board (IRB) promptly and provide the reason(s) for the termination. Previously dosed subjects will be assessed through all planned study visits.

11 STATISTICAL METHODS

11.1 General Considerations

Before unmasking the data for subjects included in this trial for the interim analysis, a statistical analysis plan (SAP), which will provide the technical details of the statistical analyses outlined here, will be prepared, finalized, and signed.

In general, data will be summarized by means of summary statistics. Continuous data will be presented as the number of observations, mean, standard deviation (SD), minimum, Q1, median, Q3, and maximum. Categorical data will be presented as counts and percentages. The data will be presented for each treatment group by visit. All data summarized will be presented in patient listings.

11.2 Analysis Sets

The **Enrolled Set** will consist of all patients enrolled in the study, ie, all patients who signed the informed consent form. This set will be used for summaries of disposition for all patients enrolled.

The **Full Analysis Set (FAS)** will include all patients for whom treatment regimen has been assigned. The FAS will be used for all analyses of efficacy endpoints. Patients will be analyzed according to the randomized treatment. Different strategies will be applied for handling data following intercurrent events (IE) (see [Section 11.3.3.1](#)). Unless stated otherwise, all subject listings will be presented using this set.

The **Safety Set (SS)** will include all patients who receive at least 1 dose of study drug. Patients will be analyzed according to treatment received. The SS will be used for analyses of safety endpoints.

The **Pharmacokinetic Set (PKS)** will include patients in the SS who have at least 1 postdose evaluable plasma ranibizumab concentration value. Patients will be analyzed according to treatment received. For cases in which a PD is identified to potentially affect plasma level, the identified concentration values will be flagged as non-evaluable and excluded from the analyses.

A blinded data review meeting (BDRM) will be held prior to database lock and unblinding of the interim analysis to agree upon the PKS, PK samples/parameters to be included in the analyses, and any data to be excluded from the FAS analyses due to IEs. All patients for whom data were impacted due to the COVID-19 pandemic will be identified as well as the data points affected. Such data will be recorded as a protocol deviation and will be assessed at the BDRM along with all other PDs with respect to

potential to affect the efficacy results. Attendees will include appropriate individuals from the Sponsor and Syneos Health. Details regarding the data to be reviewed at the meeting will be documented in the SAP and a separate BDRM plan.

11.3 Planned Analyses

11.3.1 Patient Disposition

Screen failures (with reasons), randomization, and dosing with study drug will be summarized for the Enrolled Set.

Study completion and early termination (with reasons) as well as attendance at each visit will be summarized for the FAS.

Inclusion in each analysis set will be summarized, along with reasons for exclusion.

11.3.2 Demographic and Other Baseline Characteristics

Demographics and key baseline characteristics will be summarized.

11.3.3 Efficacy Endpoints

11.3.3.1 Primary Efficacy Endpoint

The primary endpoint of the study is the change in BCVA letters at Week 8 compared to Baseline using the Early Treatment Diabetic Retinopathy Study (ETDRS) protocol for the study eye.

Due to the increase in protocol deviations related to the COVID-19 pandemic and following the recent ICH E9 (R1) Addendum¹⁹, the primary and secondary estimands of the study related to efficacy are detailed in this section. These estimands were not explicitly defined in earlier versions of the protocol (see [Section 18](#)) but the estimand framework provides a more comprehensive approach to show the impact of Covid-19 in the analysis²⁰. The presence of such IEs in a biosimilarity study may introduce potential bias and a dilution of treatment differences (i.e. increasing the chance of proving equivalence), as such the ordering of the estimands described below (in terms of primary and secondary) are chosen.

For the primary estimand, the scientific question of interest is the between-group difference (Xlucane v Lucentis[®]) in the mean change from baseline in BCVA letter score at Week 8 in patients who fulfil the study eligibility criteria, have no IEs up to and including the Week 8 BCVA assessment and complete 8 weeks of treatment of study drug (given as a single ophthalmic IVT injection every 4 weeks/monthly).

IEs are defined as:

- Early discontinuation of study treatment. Subsequent missing data (missing or collected) will be imputed in the analysis with a hypothetical strategy.
- Non-adherence with the protocol which would potentially affect the efficacy results. Such identified data at the BDRM (missing or collected) will be imputed in the analysis with a hypothetical strategy.
- Start of anti-VEGF treatment in the fellow eye. Subsequent data (missing or collected) will be imputed in the analysis with a hypothetical strategy.

The secondary estimand of the study for the primary endpoint will use alternate methods of handling data following IEs compared to the primary estimand. This approach will use a treatment policy with respect to IEs such that any data collected following the IE will be used in the analysis. So the scientific question of interest is the between-group difference (Xlucane v Lucentis[®]) in the mean change from baseline in BCVA letter score at Week 8 in patients who fulfil the study eligibility criteria and complete 8 weeks of treatment of study drug, regardless of any other IEs. However, because the study design does not plan for assessments following early treatment discontinuation, a true treatment policy strategy is not possible to apply. As such, any missing data following early treatment discontinuation will be imputed using a hypothetical strategy.

Assumptions for imputing missing data due to IEs and analysis methods for each estimand are detailed in [Section 11.3.7](#).

The change in BCVA letters at Week 8 compared to Baseline using the ETDRS protocol will be analyzed using a mixed model for repeated measures (MMRM). An MMRM approach will be fitted with geographical region of the country where enrolled, visit, eye color (light iris vs dark iris), treatment, and treatment-by-visit interaction as fixed effects, with the baseline BCVA letters and baseline BCVA letters-by-visit interaction as covariates. The treatment differences from the model at Week 8 will be evaluated and a 95% or 90% two-sided CI for the least squares mean difference between groups will be calculated. To prove the 2 products to be biosimilar, the confidence limits for this difference have to be within the equivalence margin of ± 3.5 letters for the primary estimand. The secondary estimand analysis will be supportive of the primary estimand analysis.

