8.3.2 Inclusion Criteria

To be eligible for study entry, subjects must satisfy **all** of the following inclusion criteria:

1. Written and signed informed consent form obtained at Screening before any study-related procedures are performed. Patients must be capable of providing their own consent (an impartial witness must be present in case of illiterate patients).
2. Willingness and ability to undertake all scheduled visits and assessments as judged by the investigator.

3. Newly diagnosed, active subfoveal choroidal neovascularization (CNV) lesion secondary to age-related macular degeneration (AMD) in the study eye. *Note:* active CNV indicates the presence of leakage as evidenced by fluorescein angiography (FA) and intra- or subretinal fluid as evidenced by optical coherence tomography (OCT), which *must be confirmed by the central reading center during Screening:*
 - a. The area of CNV must be $\geq 50\%$ of the total lesion area in the study eye, and
 - b. Total lesion area ≤ 9.0 disc areas (DA) in size (including blood, scars, and neovascularization) as assessed by FA in the study eye
4. BCVA of ≤ 73 and ≥ 49 ETDRS letter score in the study eye using the ETDRS chart (20/40 to 20/100 Snellen equivalent) at Screening.
5. Fellow eye should not be expected to need any anti-VEGF treatment for the duration of study participation based on Investigator's decision.
6. Age ≥ 50 years at Screening.
7. Male and female subjects of childbearing potential must be willing to completely abstain or agree to use an appropriate method of contraception from the time of signing the informed consent form and for the duration of study participation through 3 months after the last dose of study drug. See [Appendix 17.1](#) for examples of acceptable contraception. (The investigator and each subject will determine the appropriate method of contraception for the subject during the participation in the study.)
 - a. A woman of childbearing potential is any woman, regardless of sexual orientation, who meets the following criteria: 1) has not undergone a hysterectomy or bilateral oophorectomy or 2) has not been naturally postmenopausal for at least 12 consecutive months (ie, has had menses at any time in the preceding 12 consecutive months).
 - b. A man of sexual potential is any man who has not been surgically sterilized (eg, has not undergone bilateral orchiectomy).

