9.1 Pre-treatment

9.1.1 Screening Visit (Visit 1)

- Subjects will provide written informed consent before any study-related procedures may be performed.
- Assess for eligibility (against the inclusion and exclusion criteria).
- Collect full medical history, historical disease data, diagnostic information, and concomitant illnesses/diseases, adverse events (including Baseline events), and concomitant medications.
- Record demographic data, such as ethnic origin, date of birth, and sex.
- Perform a physical examination (PE), including body mass index (height and weight measured). A PE will consist of a routine evaluation of organ systems (including head, ears, eyes, nose, throat, neck, cardiovascular, pulmonary, abdomen, skin, extremities, neurological, lymph nodes, and musculoskeletal).

- At the Screening Visit, the PE will include the collection of the subject's eye color (ie, light iris or dark iris).
- Perform BCVA assessment using the ETDRS at 4 meters, including manifest refraction.
- Perform FA and OCT in both eyes, in which results should be submitted to and confirmed by the central reading center *prior* to Randomization.
- Perform CFP in both eyes.
- Perform SLE of the anterior segment in both eyes.
- Perform dilated fundus examination of the posterior segment in both eyes.
- Measure IOP in both eyes. Goldmann tonometry should be used for pre-injection IOP.
- Record vital signs including blood pressure and heart rate. Systolic and diastolic blood pressure and pulse rate will be measured after patients have been at rest (seated) for at least 5 minutes.
- Collect blood sample for hematology and clinical chemistry tests.
- For females of childbearing potential only, collect urine sample for pregnancy test.
- Record any Baseline events and concomitant medications.

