9.2 Treatment Period

9.2.1 Day 0 Visit (Visit 2) - Baseline

The Day 0 Visit (Visit 2) will take place after the Screening Visit (Visit 1). The following procedures will be performed before injection:

- Reassess/confirm eligibility against the inclusion and exclusion criteria.
- Confirm receipt of the central reading center's interpretation(s) of FA and OCT from Screening.
- Perform BCVA assessment using the ETDRS at 4 meters, including manifest refraction.
- Perform SLE of the anterior segment in both eyes.
- Perform dilated fundus examination of the posterior segment in both eyes.
- Measure IOP in both eyes, using the Goldmann tonometry method.
- Perform OCT in both eyes.
- Record vital signs including blood pressure and heart rate. Systolic and diastolic blood pressure and pulse rate will be measured after patients have been at rest (seated) for at least 5 minutes.
- Collect blood sample(s) for immunogenic (ie, anti-ranibizumab antibodies and NAb) evaluations.
- **PK subgroup only:** Collect additional blood sample(s) for PK evaluations ≤ 60 minutes before the first dose.
- Record any changes in adverse events and concomitant medications.

- Randomization will take place for eligible subjects, and each will receive a subject number. The receipt and review of the lab report is necessary before randomizing a subject.

When all the above Day 0 (Visit 2) procedures have been performed/confirmed, the study drug will be administered as an IVT injection to the subject in the study eye only. The following shall be performed after injection:

- Monitor the subject (after injection) for at least 60 minutes.
- Measure IOP in the study eye. After IVT injection (eg, 30 minutes post injection), non-contact tonometry may be used, but in the event IOP is greater than 36 mm Hg, it is recommended to perform another IOP measurement with Goldmann or Tonopen or ICare (applanation tonometer) within the next 30 minutes.
- Record any AEs, including any ISRs.

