9.3 Duration of Treatment

The duration of treatment will be approximately 52 weeks, including follow-up. Pre-treatment screening assessments shall occur within 21 days before the start of treatment.

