11.4 Determination of Sample Size

The change in BCVA after 8 weeks was evaluated from previous studies based on similar patient populations. There was a wide range of SD across the studies, ranging from 8.58 letters to 11.83 letters.

For the purpose of sample size calculation, an SD of 10 letters will be assumed for this study. This is based on an analysis of the data from clinical trials of the originator product demonstrating a clear correlation between baseline BCVA and the SD of the change of BCVA at Week 8. Considering that a narrower inclusion criterion for BCVA is being applied in this study compared to the studies of the originator product, it is expected that a baseline BCVA of around 60 letters will be observed. Therefore, an SD of 10 for the primary endpoint is well in the upper range of what is expected.

From 580 randomized patients there will be >90% power to show equivalence (ie, two-sided 95% CI for the mean difference between Xlucane and Lucentis® is confined within the equivalence margin of ± 3.5 letters) if the SD is no more than 10.

The power calculations were performed using SAS® (Version 9.3, SAS Institute Inc., Cary, NC, USA).

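### The primary BCVA model leaves out the Screening BCVA, a second pre-treatment reading held on every randomised subject: a small, optional gain in precision, not an error

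*Combined protocol and SAP*

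**What the plan says.** - **Model.** Section 11.3.3.1 fits region, visit, eye color, treatment and treatment-by-visit, "with the baseline BCVA letters and baseline BCVA letters-by-visit interaction as covariates". The synopsis gives the same model. Section 11.3.7, listing what informs the model, also names a single baseline BCVA score; the scores at other visits that it mentions are most naturally the post-baseline responses.
- **First reading.** At Screening (9.1.1) the instruction is "Perform BCVA assessment using the ETDRS at 4 meters, including manifest refraction". Inclusion criterion 4 (8.3.2) needs this value: 49 to 73, "letter score in the study eye using the ETDRS chart".
- **Second reading.** The same assessment is repeated before the first injection at the visit headed "9.2.1 Day 0 Visit (Visit 2) - Baseline". Section 11 does not itself define baseline; this heading is why it is read here as Day 0.
- **Gap.** Section 9.3: "Pre-treatment screening assessments shall occur within 21 days before the start of treatment".
- **Planning figures.** Section 11.4: "an SD of 10 letters will be assumed for this study", with earlier studies "ranging from 8.58 letters to 11.83 letters". It concludes: "From 580 randomized patients there will be >90% power to show equivalence".

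No reason is given for leaving Screening BCVA out. Section 11.1 defers technical detail to an SAP to be signed before the interim unmasking. The document reviewed contains no separate SAP text.

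**The concern.** A single acuity reading carries measurement error. The error in the Day 0 reading enters every change score with a minus sign, and adjusting for Day 0 BCVA removes only part of it. A second untreated reading of the same eye helps to separate true starting acuity from Day 0 error, so it should lower the residual variance of the Week 8 contrast.

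The Screening value precedes randomisation, so using it changes neither the endpoint nor the treatment effect being estimated. Equivalence is decided by whether a confidence interval fits inside ±3.5 letters, so its width is what counts. What is at stake is how much narrower it could be without collecting anything new.

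**Working it through.** **1. The plan's own power.** Inputs from 11.4: 580 randomised (290 per arm), SD 10, margin 3.5, two-sided 95% CI. True difference 0 is assumed, since none is stated.

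- SE = 10 × √(2/290) = 0.830
- 95% half-width = 1.96 × 0.830 = 1.63 letters
- Power = 2Φ(3.5/0.830 − 1.96) − 1 = 97.6%

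This agrees with the stated figure of more than 90%. With 20% loss (assumed; 232 per arm) it is 93.0%. At SD 11.83 and 290 per arm it is 89.1%.

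**2. A model for the two readings.** None of these ranges is in the documents:

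- true acuity SD τ = 6-10 letters, before selection on Screening to 49-73, centred at 60
- reading-error SD e = 2-5 letters
- true drift SD w = 0-5 letters between Screening and Day 0
- SD of the Week 8 change fixed at 10 (variance 100)

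Only the Day 0 error links the change score to the two readings. Hence:

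- residual variance given Day 0 = 100 − e⁴ / Var(Day 0)
- residual variance given Day 0 and Screening = 100 − e⁴ / (V + e²), where V = τ²e²/(τ² + e²) + w²

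Var(Day 0) is taken after the 49-73 restriction.

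*Favourable corner* (τ = 10, e = 5, w = 0): V = 20 and Var(Day 0) = 71.2. Residual variance goes from 100 − 625/71.2 = 91.2 to 100 − 625/45 = 86.1, a 5.6% reduction.

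*Unfavourable corner* (τ = 6, e = 2, w = 5): V = 28.6 and Var(Day 0) = 56.25. Residual variance goes from 100 − 16/56.25 = 99.72 to 100 − 16/32.6 = 99.51, a 0.2% reduction.

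**3. Results at 290 per arm, true difference 0.** Equivalent subjects = 580r/(1 − r) for variance reduction r.

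| τ, e, w | Variance reduction | 95% half-width | Equivalent subjects | Power |
|---|---|---|---|---|
| 6, 2, 5 | 0.2% | 1.625 → 1.624 | 1 | 97.6% → 97.6% |
| 6, 2, 3 | 0.6% | 1.624 → 1.620 | 3 | 97.6% → 97.7% |
| 6, 3, 5 | 0.6% | 1.617 → 1.612 | 4 | 97.8% → 97.8% |
| 6, 3, 2 | 2.0% | 1.611 → 1.595 | 12 | 97.8% → 98.1% |
| 6, 4, 0 | 3.7% | 1.578 → 1.549 | 22 | 98.3% → 98.6% |
| 10, 5, 3 | 4.1% | 1.563 → 1.531 | 25 | 98.5% → 98.8% |
| 10, 5, 0 | 5.6% | 1.555 → 1.510 | about 35 | 98.6% → 99.0% |

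Simulation with the 49-73 restriction gives the same picture: up to 6.0% with a wider true SD of 12.

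**4. Where power is tighter.** Power = Φ((3.5 − δ)/SE − 1.96) + Φ((3.5 + δ)/SE − 1.96) − 1. Variance reductions of 2.0% and 5.7% are applied, and the gain already taken by Day 0 adjustment is ignored:

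- SD 11.83, δ = 0: 89.1% → 89.9% and 91.2%
- SD 10, δ = 1 letter: 85.3% → 86.0% and 87.3%

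At a 0.5% reduction each rises by only about 0.2 points.

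**5. Cost in precision.** One more parameter at about 570 degrees of freedom costs about √(570/569) − 1 = 0.1% in SE. That uses up most of the gain in the least favourable corner and is negligible elsewhere.

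**The case against.** The strongest reply is that nothing is wrong. The plan adjusts for the outcome's own baseline with a visit interaction, stratifies randomisation on it, and yields a valid interval. That stands. A reader might infer that the interval is mis-specified or biased; the documents do not support this.

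A reader might also take it as established that the planned interval is wider than it need be. That is not shown. The gain rests on reading error and drift, for which the documents give no figure. It fades as reading error falls or as acuity changes over up to 21 untreated days, and these are eyes with newly diagnosed active lesions. The upper end needs large reading error and no drift. This stands, and it is why the range runs down to a fraction of a percent.

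Nor do the figures support inferring that the equivalence conclusion is at risk. The protocol regards SD 10 as towards the high end of expectation, and power is below 90% before covariate adjustment only close to the largest SD it cites.

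Finally, a Screening-by-visit term might seem necessary for the gain to reach Week 8. In the model above, Screening informs only the Day 0 error, which enters every change score equally. Simulated coefficients at two visits were 0.357 and 0.355 in one setting, 0.445 and 0.443 in another. A main effect suffices there.

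Two smaller points also stand. Data set aside after intercurrent events mean that freedom from bias leans on missing-at-random as well as on randomisation, as it already does in the planned model. And the SAP may already settle the matter. None of this removes the observation that a pre-randomisation reading held on everyone goes unused.

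**Conclusion.** The point holds as a missed efficiency of low priority. Under the assumed ranges:

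- The Week 8 residual variance falls by about 0.5-6%, or about 0.2% where reading-error SD 2 meets drift SD 5.
- The interval is about 0.3-3% narrower: 0.005-0.045 letters off the 95% half-width, equivalent to about 3-35 subjects. The extreme corner gives less.
- Power rises by under 0.5 points at SD 10 with no true difference, and by up to about 2 points with a 1-letter difference or an SD near 11.83.

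The conclusion would seldom change. The existence of the second reading and its absence from the model as written come from the documents; the size of the benefit rests on assumption.

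**What to change.** Optional. Before the interim unmasking:

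- Add Screening BCVA as a covariate in the BCVA repeated-measures model (synopsis, 11.3.3.1, 11.3.7) and in the ANCOVA sensitivity models.
- For rescreened subjects (8.3.1), use the latest Screening value.
- Keep the endpoint as change from Day 0 and leave all other terms as they are. State in section 11 that baseline means Day 0.
- A Screening-by-visit term may be added to match the baseline-by-visit term, but it is not shown to be needed for the gain.

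The cost is one covariate (about 0.1% in SE) and a small edit to the pre-specified model, with no new data or procedure. Added after unmasking, it would be post hoc and should not then enter the primary analysis.
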